6.2 Secondary objectives

- Understanding the acceptability and effectiveness of VR interventions in office gynaecology procedures
- Understanding the factors that might influence the willingness of patients to participate in a future formal trial of the technology.
- Understanding how best to implement the technology and designing of the contents of the VR intervention.

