7.1 Inclusion criteria

Patients: Clinical indications for undergoing an MVA will be confirmed.

Inclusion criteria will include all women of 18 - 50 years of age, planned for a MVA who are able and willing to give informed consent.

Staff: Inclusion criteria will include the clinician performing the MVA and the nurse supporting the clinic.

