7.2 Exclusion criteria

Patients:

- Hearing impairments and blindness
- History of epilepsy or any previous seizures
- History of claustrophobia
- Any known anatomical characteristics that may make performing the office procedure more difficult (e.g., cervical conisation)
- Any known characteristics that make the patient unsuitable for undergoing MVA (e.g. known bleeding disorder, gestation >12 weeks)
- The denial or withdrawal of informed consent

Staff: The denial or withdrawal of informed consent

8. Study design

The study is a prospective trial involving mixed methods of qualitative and quantitative analysis. The study will include 30 patients attending for MVA who will be offered inclusion in the study at the time of booking the procedure.

They will be given a study information sheet, an invitation to participate with a reply slip to indicate whether they would like to participate in the study. Patients will be given standard pre-procedural information about the procedure as per standard practice. Written informed consent will be obtained from participants and the interview outputs will be anonymised.

Virtual Reality in Manual Vacuum Aspiration. Version 8.0. 27/02/2021 Page 10 of 19

All patients will fill in a questionnaire before and after the procedure and the 15 patients who use the virtual reality headset will have a semi-structured interview regarding their experience. This will be audio recorded. The interview will last approximately 10 minutes.

The staff in the clinic will include a clinician performing the procedure and a staff nurse supporting the clinic to whom both will be given a study information sheet regarding the study and a written informed consent for a questionnaire will be obtained from them if they agree to participate. The clinician performing the procedure will fill in a questionnaire per patient regarding the ease of the procedure and perceived pain levels of the patient. The Clinician performing the procedure and nursing staff's perception regarding feasibility of using the VR equipment for each patient who had the intervention will also be assessed through the questionnaire.

Patient follow up will not be routinely arranged for the purpose of the study. Routine follow up as per clinical requirements will be arranged as routine for the procedure performed.

9. Study procedures

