The study will recruit 30 patients to use VR during MVA. On confirmation of consent the patients will be allocated to VR intervention group or no intervention standard care for MVA control group. 15 patients will be recruited to each group across both sites. Allocation to control or intervention will be performed by computer-generated randomisation. All patients will receive the same analgesia as per standard MVA protocol using para-cervical block.

The VR intervention will involve watching a standard content of the video on a mobile device using a VR headset to distract them during the procedure. The duration of the video will be 15 minutes; but the video will only be played for the duration of the MVA. Patients are allowed to stop viewing the video if they so desire and this will be recorded. If the MVA lasts longer than the VR experience the programme can be restarted and watched again.

Patients in both groups will fill pre and post procedural questionnaires. Pain and anxiety scores prior to and after the procedure will be evaluated. Scores will be measured by a Numeric Rating Scale (NRS) which is a validated measure of pain which is easy to use, has high compliance rates and detects meaningful changes in pain ¹³.

A semi-structured interview will be conducted with the VR intervention group patients each lasting approximately 10 minutes. The semi-structured interviews will allow for participants to be asked similar questions within a flexible framework ^{14,15}. The interviews will be conducted within 30 minutes of the procedure, in a suitable location and will be recorded on a digital voice recorder. The questions will be focused on the women's experiences of the procedure, their pain perception, anxiety levels and questions around the VR intervention as well as any other aspect of their hospital care they felt to be relevant. If further clarification or exploration of any particular aspect of their care was required, the interview will readdress these topics before the end of the interview. Interviews will continue until no new information is obtained, indicating that

Virtual Reality in Manual Vacuum Aspiration. Version 8.0. 27/02/2021 Page 11 of 19

the theoretical saturation point has been reached ¹⁶.

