Clinician and nursing staff's perception regarding feasibility of using the VR equipment will also be assessed through a questionnaire. The clinician questionnaire will also assess the ease of the procedure and perceived pain scores for the patient.

Patient follow up will not be routinely arranged for the purpose of the study. Routine follow up as per clinical requirements will be arranged as routine for the procedure performed.

Patients and staff can withdraw from the study if they so desire at any time and without giving a reason. A decision to withdraw at any time, or a decision not to take part, will not affect the standard of care or treatment that they receive.

The study will end once the proposed numbers of patients have been recruited and data analysis completed. Participants will be debriefed after their participation in the study and will be directed to suitable support agencies if necessary.

10. Assessment and management of risk

Possible risks of participation in the study include the potential to experience the side effects of nausea, headaches and motion sickness during the use of VR programme. Approximately 25-40% of users of VR experience these symptoms. The risks are greater with prolonged use of more than 30 minutes ¹². VR is a known trigger for seizures in those with a history of epilepsy, for this reason women with any history of seizures or epilepsy will be excluded from the study.

Participants will be informed of these risks at the time of invitation to the study and details will be included in the patient information leaflet. Any participant wishing to end the VR programme may do so at anytime and this will be recorded.

11. Statistical considerations

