11.1 Sample size

The study will include 30 patients with 15 patients in the VR intervention group and 15 patients in the MVA standard care control group.

• 11.2 Method of analysis

The recruitment of women and interviewing will proceed alongside data coding and preliminary analysis.

The statistical analysis will include statistical comparison of pre and post anxiety and pain scores. Interview analysis will be performed by the chief investigator and/or study manager. Interviews will be transcribed verbatim and initially coded by reading and re reading the transcript and making notes, drawing on the observations made during the interviews and transcription. Transcripts will be coded line-by-line, describing,

Virtual Reality in Manual Vacuum Aspiration. Version 8.0. 27/02/2021 Page 12 of 19

summarising and attending to linguistic elements such as pronoun and metaphor use. The transcripts will be entered into a qualitative software package (N6) and a thematic analysis undertaken from the emergent themes developed from these codes and cluster with related themes. Initial coding is Initial phase, which involves open coding. Axial coding and selective coding with use of constant comparison will enable a cyclical and iterative process on the principles of grounded theory. Analytic frame for the analysis will be linked to the primary and secondary aims.

Staff questionnaires will be analysed to correlate pain scores of actual vs. perceived and feasibility of carrying out the intervention will be assessed.

Demographic data would include age, parity and ethnicity.

Data and all appropriate documentation will be stored for a minimum of 20 years after the completion of the study, including the follow-up period.

12. Ethics

The Chief Investigator will obtain approval from an NHS ethics committee. The Chief Investigator will require a copy of the Trust R&D approval letter before accepting participants into the study. The study will be conducted in accordance with the recommendations for physicians involved in research on human subjects adopted by the 18th World Medical Assembly, Helsinki 1964 and later revisions.

Consent

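### Minor: section 11.2 only correlates clinician-perceived with patient-reported pain, which does not show the size or direction of a systematic gap; the paired difference should be reported as well.

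*Combined protocol and SAP*

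**What the plan says.** The clinician's rating is collected patient by patient. Section 8 states: "The clinician performing the procedure will fill in a questionnaire per patient regarding the ease of the procedure and perceived pain levels of the patient". Section 9 repeats the content: "The clinician questionnaire will also assess the ease of the procedure and perceived pain scores for the patient". Neither section gives the scale of the clinician's item or the moment to which it refers.

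On the patient's side, section 9 says: "Pain and anxiety scores prior to and after the procedure will be evaluated". Section 15.2 describes the patient's pain scale as a numeric rating scale with integers from 0 to 10.

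Section 11.2 names two quantitative analyses of these scores. The first is: "The statistical analysis will include statistical comparison of pre and post anxiety and pain scores". It does not mention the clinician's score. The second is the one at issue: "Staff questionnaires will be analysed to correlate pain scores of actual vs. perceived". No coefficient is named, and the plan does not say which patient score counts as the actual one.

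**The concern.** Setting actual against perceived pain most naturally asks whether clinicians judge pain correctly, and if not, in which direction and by how much. A correlation answers a different question: whether patients who report more pain are also the ones whom clinicians rate higher. A team that always scores three points too low can do that perfectly well.

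An analyst who followed section 11.2 to the letter would report a coefficient and stop. A reader could then take a high value as evidence that clinicians gauge pain accurately, which the coefficient cannot establish. At stake is the interpretation of one ancillary result, for which the paired data are already planned.

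**Working it through.** The plan gives no figure for this analysis and no power, alpha, SD or effect size for its sample size, so there is no calculation to reproduce. The only stated number is 15 + 15 = 30 patients (section 11.1), hence at most 30 pairs.

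**1. Effect of a constant gap.** Let P be the patient's score and C the clinician's. For any constant a, cov(P, C + a) = cov(P, C) and SD(C + a) = SD(C), so r is unchanged, while the mean of (C + a - P) moves by exactly a.

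As a constructed illustration (not trial data), take the patient scores 3, 4, 5, 6, 7, 8, 9, 5, 6, 7, repeated three times (n = 30, mean 6.0). The clinician's score is the patient's plus 0, 1, -1, 0, 1, -1, 0, 0, 1, -1 in the same order, plus a shift. All scores stay within 0 to 10.

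| Shift | Pearson r | Spearman rho | Mean difference (clinician minus patient) |
|---|---|---|---|
| 0 | 0.900 | 0.895 | 0 |
| -1 | 0.900 | 0.895 | -1 |
| -2 | 0.900 | 0.895 | -2 |
| -3 | 0.900 | 0.895 | -3 |

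A proportional error is hidden too. If each clinician score is exactly half the patient's, r = 1.0 and the mean difference is 0.5 × 6.0 - 6.0 = -3.0.

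**2. Does the bounded scale change this?** With rounding and limits at 0 and 10 the invariance is only approximate. Assumed inputs, none of them in the documents: patient mean 5 and SD 2.5, clinician noise SD 1.2, 20,000 simulated samples of 30.

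| True underestimation | Mean r | Mean paired difference |
|---|---|---|
| 0 | 0.89 | 0.00 |
| 1 | 0.89 | -0.93 |
| 2 | 0.88 | -1.82 |
| 3 | 0.85 | -2.64 |

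The Fisher interval is tanh(atanh r ± 1.96/√(n - 3)). For r = 0.89 and n = 30 this is tanh(1.422 ± 0.377) = 0.78 to 0.95. A fall from 0.89 to 0.85 lies well inside that, so r would give no usable signal of a three-point gap.

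**3. What the paired difference would deliver.** The 95% CI half-width is t(29) × SD/√30, with t(29) = 2.045. The SD of the differences is assumed.

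| Assumed SD | Half-width, n = 30 |
|---|---|
| 1.5 | 0.56 |
| 2.0 | 0.75 |
| 2.5 | 0.93 |
| 3.0 | 1.12 |

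These figures require complete and independent pairs. For comparison, a correlation of 0.5 at n = 30 has a 95% CI of tanh(0.549 ± 0.377) = 0.17 to 0.73.

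**The case against.** Three objections carry weight.

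*The question may be association.* Whether clinicians recognise which patients are in more pain is a legitimate question, and correlation addresses it. Section 11.2 does not say that agreement is the aim. This stands, and is why the correlation should be kept.

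*The wording may be loose.* With no coefficient named, the verb may simply mean compare. This also stands. In that case the plan is under-specified rather than mistaken, and the added sentence only makes the intention explicit.

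*Little depends on it.* The secondary objective that comes nearest is "Understanding the acceptability and effectiveness of VR interventions in office gynaecology procedures", and it concerns the intervention, not clinicians' judgement of pain. No decision rule uses the result.

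A reader might go further and infer that the plan has chosen a wrong method that puts the trial's conclusions at risk, or that the two pain items are mismatched. The documents support neither. No primary conclusion uses this comparison. The questionnaires are not in the documents, so the clinician item's scale and reference period cannot be checked; that is a condition on the remedy, not a fault. Nor does anything in the documents show that clinicians do under-rate or over-rate pain; the gaps above are illustrations.

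**Conclusion.** A minor point and a cheap improvement. Correlation is the only analysis named for these pairs, and taken alone it cannot show whether clinicians score too high or too low, or by how much. That property of the method needs no assumption about the trial when the gap is constant and scores stay within the scale. The near-invariance on a bounded scale, and the precision of about 0.6 to 1.1 points, rest on assumed SDs.

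Two limits apply to the precision. Staff complete questionnaires only if they consent, so there may be fewer than 30 pairs. The staff criterion is "Staff: Inclusion criteria will include the clinician performing the MVA and the nurse supporting the clinic", with no number of clinicians given. One clinician may therefore rate several patients, and an interval that treats pairs as independent may be too narrow.

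**What to change.** Add to section 11.2:

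> For all available pairs, the difference between clinician-perceived and patient-reported pain (clinician minus patient) will be reported as the mean with 95% CI and the median, together with its spread (limits of agreement) and a plot of difference against mean; the correlation will be reported alongside. The CI assumes independent pairs and may be too narrow where one clinician rates several patients.

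This applies only if the clinician's item uses the same 0-10 numeric rating scale and the same reference period as the patient's. That should be confirmed from the questionnaires, and section 11.2 should then name the matching patient score. If the items differ, the paired difference should not be reported as it stands; aligning them would mean rewording one item, which may need an amendment.

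Reporting the mean, the median and the plot together avoids any rule for switching summaries after the data have been seen. The cost is a little more analysis of data already planned, with no new data item and no change to the sample size.

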Consent to enter the study will be sought from each participant only after a full explanation has been given, an information leaflet offered and time allowed for consideration. Signed participant consent will be obtained. The right of the participant to refuse to participate without giving reasons will be respected. After the participant has entered the study the clinician remains free to give alternative treatment to that specified in the protocol at any stage if he/she feels it is in the participants' s best interest, but the reasons for doing so will be recorded. In these cases the participants remain within the study for the purposes of follow-up and data analysis. All participants are free to withdraw at any time from the protocol treatment without giving reasons and without prejudicing further treatment.

Confidentiality

Information related to participants will be kept confidential and managed in accordance with the Data Protection Act, NHS Caldecott Principles, The Research Governance Framework for Health and Social Care, and the conditions of Research Ethics Committee Approval.

Conflicts of interest The CI and PI have no conflicts of interest.

13. Public Involvement

Virtual Reality in Manual Vacuum Aspiration. Version 8.0. 27/02/2021 Page 13 of 19

The inspiration for this study was a patient's inquiry about using her own VR headset during MVA. They subsequently aided in the study design, choosing of video content and the VR device. Informal feedback from patients offered the VR device during MVA procedure include "good distraction"; "visual nature goggles helped so I didn't watch or listen" and "wouldn't want to see the procedure".

14. Data handling and record keeping

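### Section 11.2 correlates clinicians' pain ratings with patients' scores without separating or adjusting for arm, and a correlation cannot show under-rating

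*Combined protocol and SAP*

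**What the plan says.** The analysis is set out in one clause of section 11.2: "Staff questionnaires will be analysed to correlate pain scores of actual vs. perceived". The clause names no coefficient, test or interval, and says nothing about arm or about several ratings by one clinician. It also does not say which patient score counts as the actual one.

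The rest of the design comes from other sections:

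- Section 11.1: "The study will include 30 patients with 15 patients in the VR intervention group and 15 patients in the MVA standard care control group".
- Section 9: "Allocation to control or intervention will be performed by computer-generated randomisation". No blinding is described.
- Section 8: "The clinician performing the procedure will fill in a questionnaire per patient regarding the ease of the procedure and perceived pain levels" of that patient. The feasibility items are limited to VR patients ("perception regarding feasibility of using the VR equipment for each patient who had the intervention will also be assessed through the questionnaire"). The pain rating carries no such limit, so it is collected in both arms.
- Section 9: VR patients watch the video "using a VR headset to distract them during the procedure", so the operating clinician can see who is in the VR arm.
- Section 15.2: patients score pain on a 0 to 10 numeric rating scale. The scale for the clinician's rating is not stated.

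**The concern.** VR is being studied because it may lower pain. If it does, and a clinician who sees the headset expects less pain, both scores fall together in the VR arm. A correlation over all 30 patients would then be positive even if clinicians could not tell one woman's pain from another's within an arm. It would be read as clinician accuracy when part of it is an arm difference.

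The measure itself is also limited. A correlation ignores level, so a uniform under-rating of pain leaves it unchanged. It cannot show whether clinicians miss more pain when the woman wears a headset. That question bears on how best to implement the technology, a secondary objective in section 6.2, and the data to describe it are already being collected in both arms.

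**Working it through.** The plan states no correlation, power or interval for this analysis, so there is no figure to reproduce.

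**Inputs.** From the documents: 30 patients, 15 per arm (section 11.1). Assumed, because the documents give no values: dx, the arm shift in the patient's score; dy, the arm shift in the clinician's rating; and r_w, the within-arm correlation. Shifts are in within-arm SDs.

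**1. Effect of pooling.** With 1:1 allocation, the arm shifts add dx²/4 and dy²/4 to the two variances and dx·dy/4 to the covariance:

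pooled r = (r_w + dx·dy/4) / √[(1 + dx²/4)(1 + dy²/4)]

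No within-arm association (r_w = 0), same-direction shifts:

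- 0.5 and 0.5: 0.0625/1.0625 = 0.06
- 0.8 and 0.8: 0.16/1.16 = 0.14
- 1.0 and 1.0: 0.25/1.25 = 0.20

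Some within-arm association (r_w = 0.3):

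- 0.8 and 0.8: 0.46/1.16 = 0.40
- 1.0 and 1.0: 0.55/1.25 = 0.44
- 0 and 0.8 (clinician's rating alone shifts): 0.30/√1.16 = 0.28
- 0.8 and −0.8 (opposite shifts): 0.14/1.16 = 0.12

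Pooling can therefore raise or lower the figure.

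**2. How often it would look significant.** This applies only if the coefficient were tested, which the plan does not say. In 40,000 simulated trials of 15 + 15 with r_w = 0, a two-sided 5% test of the pooled r rejects in about 6%, 11% and 19% of trials for shifts of 0.5, 0.8 and 1.0 SD in both scores. The arm-adjusted (partial) correlation rejects in about 5% throughout.

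**3. What a correlation cannot show.** If every clinician rated every patient 2 points too low, corr(x, y − 2) = corr(x, y), so r would not change. If the extra under-rating occurred only under VR, say 0.8 SD with patients' own scores unshifted, a within-arm r of 0.50 would become 0.50/√1.16 = 0.46. A material arm-specific under-rating would barely move the coefficient. The mean of clinician score minus patient score, by arm, shows it directly.

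**4. Precision of the alternative.** A single-arm r of 0.5 with n = 15 has a Fisher-z 95% interval of tanh(0.549 ± 1.96/√12) = −0.02 to 0.81. With all 30 patients treated as independent it is tanh(0.549 ± 1.96/√27) = 0.17 to 0.73. The between-arm difference in mean gap has a standard error of √(2/15) = 0.37 SD of the gap.

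**The case against.** The strongest reply is that the clause is silent rather than wrong. It does not say that the arms will be pooled, and nothing bars a by-arm summary. That is right: the supported finding is that arm is neither separated nor adjusted for, not that one pooled figure is prescribed. The p-values in the working likewise presuppose a test that the plan does not mention.

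The size also depends on the assumptions. At 0.3 SD in both scores the pooled r is 0.0225/1.0225 = 0.02 and rejection stays near 5%. Only large shifts in the same direction in both scores give a noticeable inflation. This stands and limits the priority.

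Whether VR impairs clinicians' judgement of pain is not an objective in section 6. This too stands; the link is only to the implementation objective. The patient comment in section 13 ("visual nature goggles helped so I didn't watch or listen") concerns her own view of the procedure and is not evidence that clinicians misjudge pain.

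A reader might also infer that, because a few clinicians supply all the ratings, the error bars are too narrow and the effective sample is far below 30. The documents do not support this. No interval is planned and the number of clinicians is not given. The usual design effect, 1 + (m − 1)·ICC for m patients per clinician, applies to a mean and not to a correlation. In simulations with 30 patients shared among 2 to 10 clinicians and a within-clinician r of 0.5, the true standard error was 1.01 to 1.07 times the naive one when clinicians differed only in rating level (ICC 0.2 to 0.4). It was 1.04 to 1.37 times when patients' pain also clustered by clinician (ICC 0.1 to 0.2), and 1.14 to 1.54 times when clinicians differed in how they tracked pain (slope SD 0.3). The documents cannot say which case applies. What remains is a reason to record who rated whom.

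**Conclusion.** The point holds as a gap in the analysis plan. Ratings are made in both arms by clinicians who can see the allocation, and section 11.2 neither separates nor adjusts for arm. A figure pooled over arms could not be read as clinician accuracy. Under assumed shifts of 0.5 to 1.0 SD in both scores, it would average about 0.06 to 0.20 with no within-arm association, and other patterns of shift would lower a true positive association. The limitation that does not depend on assumed shifts is that a correlation is blind to uniform under-rating and nearly blind to under-rating confined to one arm.

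The priority is minor. This is a secondary, descriptive analysis in a feasibility study of 30 patients, and no claim about too-narrow intervals or a reduced effective sample is warranted.

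**What to change.** In section 11.2, replace the bare correlation with:

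- the association between clinician and patient pain scores adjusted for arm, using all 30 patients;
- the mean clinician-minus-patient difference in each arm, with the between-arm difference, labelled as descriptive;
- a statement of which patient score is compared, and confirmation that the clinician's rating uses the same 0 to 10 scale, since the difference needs a common scale.

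Add a clinician code to the existing questionnaire and report the number of distinct raters and the patients rated by each. If the code is not collected, repeat ratings by one clinician may not be recoverable later.

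The cost is a few sentences, one field on a form and one small table. The downside is imprecision: with 15 patients per arm, the by-arm differences will describe this sample and inform a later trial, and will not settle whether VR changes clinicians' judgement.
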